The objective of the proposed research is to evaluate a promising strategy for CPAP level selection: a physiologic approach minimizing V/Q mismatch and measured non-invasively at the infants bedside. We propose the following specific Aims and hypotheses in support of this objective: Aim 1 (primary): measure the responsiveness of V/Q mismatch to a strategy of individualized CPAP level selection. We hypothesize that V/Q mismatch will, on average, improve by 10% of baseline V/Q mismatch at the best identified CPAP level. Aim 2: describe the distribution of best CPAP levels as identified by our strategy. Best CPAP levels will be described as both absolute values and relative to baseline (+2 cm H₂O, -1 cm H₂O, etc.). For this exploratory aim, we hypothesize that a best CPAP will be identified above the baseline in greater than 50% but less than 80% of subjects. Demonstrating that most but not all infants benefit from higher pressures will highlight the importance of individualized CPAP level selection in premature infants.

Primary outcome variable(s)

Primary outcome measure: V/Q mismatch. This parameter will be calculated by computer software on the basis of the curvilinear characteristics generated by a best-fit curve connecting the FiO₂/SpO₂ pairs obtained during the study protocol. With lower V/Q and greater mismatch, the curve is progressively displaced to the right relative to a curve corresponding to an ideal reference lung (interrupted, left-most curve in Figure 2, see attached documents). The V/Q ratio is displayed on the software output after the FiO₂/SpO₂ pairs are input. Additionally, this parameter is also displayed as the degree of right-shift relative to the ideal reference lung (greater values indicate more mismatch), providing a positive continuous number with units of % FiO₂ as an alternative measure to the ratio value with greater ease of use. This will be measured twice at baseline without a change in CPAP level and then following each CPAP level change. The primary outcome measure is the responsiveness of V/Q mismatch to a strategy of individualized CPAP level selection, measured as the improvement in V/Q mismatch between the second baseline level and best identified CPAP level for each subject (see Figure 3 in attached documents.) For infants not responding to either +1 or -1 cm H₂O CPAP level changes, baseline CPAP will be defined as best, with zero assigned as the improvement in V/Q mismatch.

Secondary outcome variable(s)

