Secondary outcome: best CPAP level. Our second Aim is to describe the distribution of best CPAP levels as identified by our strategy. We hypothesize that best CPAP will vary between infants, resulting in a distribution of values. Best CPAP level will be identified as the lowest CPAP level associated with an improvement greater than 5% in V/Q mismatch relative to the preceding CPAP level, as described in the study protocol. This will be "measured" once at the conclusion of the study protocol. Excessive

airway pressures can result in lung over-distension and can plausibly result in adverse cardiopulmonary interactions through transmission of positive pressure to the heart and intra-thoracic vessels (however, this has not been observed in any modern CPAP level studies performed in premature infants, see Table 1). We will measure the impact of CPAP level changes on the following readily available clinical cardiovascular parameters during the study protocol: Mean arterial blood pressure will be measured with a neonatal blood pressure cuff used for routine clinical care and placed on an upper extremity or through pressure transduction of an indwelling arterial catheter, when present (uncommon in our subject population), with units of mm Hg. This outcome will be recorded at the end of each baseline and CPAP level period by the research team. Heart rate will be measured and displayed by the study pulse oximeter, with units of beat per minute. This outcome will be recorded at the end of each baseline and CPAP level period by the research team. Additional data to be collected will include: i) demographic data; (gestational age, birth weight, gender, race, etc.) ii) baseline variables (receipt of antenatal steroids, Apgar scores, age in hours and FiO₂ at intervention, most recent hemoglobin level, CPAP pressure source and interface, etc.) and iii) important or pertinent in-hospital neonatal outcomes (survival to discharge, BPD, brain injury by ultrasound, patent ductus arteriosus, necrotizing enterocolitis, retinopathy of prematurity, duration of: MV days, CPAP and supplemental oxygen, etc). This data will be used to explore associations between these variables and both a) baseline V/Q mismatch and b) the responsiveness of this parameter to CPAP level changes, with a goal of supporting hypothesis generation for subsequent research

Background

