This study will enroll up to 30 patients in order to evaluate 20 subjects. Infants will be screened for eligibility by the research team using routinely available clinical data from the electronic health record. Informed consent will be obtained from parents or guardians approached within the HUP ICN, PAH ICN, or the CHOP N/IICU during the eligibility window as described below. The diagram depicted in Figure 4 summarizes expected enrollment in consideration of our eligibility criteria and additional barriers to successful recruitment and study application. This estimate suggests a 10-month window of active enrollment will be required to meet our recruitment goals, making our one-year recruitment goal feasible. Aim 1 guides sample size considerations. Using a paired test of correlated means, a sample size of 20 evaluated infants will provide 80% power to detect an overall average percent change of 10% from baseline, assuming a 15% standard deviation of the difference and a two-sided alpha level of 0.05.

Key inclusion criteria

I1. 27-35 weeks corrected gestational age (CGA) by best obstetric estimate, determined by the clinical obstetric team during antepartum admission and chronologic age, measured from date of birth I2. Chronologic age greater than 24 hours, measured from time of birth. I3. On CPAP support between 4-8 cm H₂O for greater than 24 hours, as document on the bedside infant flow sheet. I4. Supplemental oxygen requirement, with a fraction of inspired oxygen (FiO₂) 0.25 for at least 2 consecutive hours, as documented on the bedside infant flow sheet. (Infants without an oxygenation requirement are unlikely to have significant V/Q mismatch. Further, FiO₂ titrations (see Procedures) are required to apply the non-invasive technique, resulting in limited applicability to infants with little or no supplemental oxygen requirement).

Key exclusion criteria

E1. Congenital anomalies, as determined by the clinical supervising physician. E2. Current or prior air leak syndrome, as determined by the clinical supervising physician.

Vulnerable Populations

Children Form

Pregnant women (if the study procedures may affect the condition of the pregnant woman or fetus) Form

Fetuses and/or Neonates Form

Prisoners Form

Other

None of the above populations are included in the research study

The following documents are currently attached to this item:

There are no documents attached for this item.

Populations vulnerable to undue influence or coercion

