
No active consideration of endotracheal intubation; as determined by the clinical Attending of record. 2. No hemodynamic instability, defined as a baseline heart rate less than 100 beats per minute (bpm) or greater than 180 bpm; or a mean arterial blood pressure of less than 30 millimeters of mercury (mm Hg). 3. No supplemental FiO₂ requirement greater than 0.45. 4. No capillary/arterial partial pressure of carbon dioxide greater than 65 mm Hg on last blood gas analysis, unless performed more than 6 hours prior. 5. No more than 6 apnea/bradycardia/desaturation events requiring tactile stimulation or more than 1 requiring positive pressure bag ventilation in the preceding 6 hours. Initiation of the study protocol will be deferred until these criteria are met. Figure 3 depicts the study protocol as applied in one hypothetical subject. Of note, the protocol will vary between subjects with respect to the direction and extent of CPAP level changes, as determined by the absence or presence of a response at each step-wise CPAP level change. This is described in detail below. Subjects will undergo the study interventions in their routine clinical environment. The clinically selected CPAP interface and pressure source will be maintained. A study pulse-oximeter, with low motion artifact and a short averaging time, will be placed on a post-ductal limb and used for SpO₂ measurements. V/Q will first be measured on two separate occasions 30 minutes apart at baseline CPAP, set by the clinical team. The repeat baseline measures will allow an estimate of the stability of V/Q as a function of time (further discussed in Confounding under Analysis Plan). To measure V/Q mismatch, gradual changes in delivered FiO₂, followed by SpO₂ measurement, will be applied to obtain three FiO₂/SpO₂ pairs, one each for SpO₂ values in the ranges of 85-87%, 89-91% and 93-95%. To obtain each SpO₂ range, FiO₂ will be titrated gradually until SpO₂ falls within the desired values. After 60 seconds of stabilization at the identified FiO₂ value, SpO₂ will be recorded every 30 seconds for 2 minutes if an adequate signal waveform is present, providing up to four SpO₂ values. These values will be averaged to calculate the SpO₂ value used for the FiO₂/SpO₂ pair, acknowledging the inherent instability of pulse-oximeter values over time in premature infants. A computer software program will immediately calculate V/Q from the identified FiO₂/SpO₂ pairs at the bedside. Next, CPAP will be increased by +1 cm H₂O. A period of 15 minutes will elapse to allow equilibration of lung volumes in response to the CPAP level change (24). V/Q calculations as described above will be repeated. A positive response will be defined as an improvement in V/Q at the new pressure level of 5% relative to the preceding CPAP level. Responders will undergo subsequent stepwise +1 cm H₂O increases up to +3 cm H₂O from baseline or 8 cm H₂O; whichever is less. Infants not responding to the initial +1 cm H₂O increase will return to baseline CPAP for 15 minutes and then be assessed at -1 cm H₂O from baseline. Infants responding at this lower CPAP level will undergo an additional decrease to -2 cm H₂O from baseline or 3 cm H₂O; whichever is greater. The allowed range of -2 to +3 cm H₂O reflects our institutional practice of typically setting a baseline CPAP level of 5 or 6 cm H₂O and a CPAP pressure range of 4 to 8 cm H₂O used in international trials. Best CPAP will be defined as the lowest (and last) CPAP level at which a positive response, as defined above, is measured. The baseline CPAP level will be defined as best for those infants not responding to either +1 or -1 cm H₂O CPAP level changes, with a corresponding V/Q improvement of zero. Upon completion of the study protocol, infants will be returned to their baseline CPAP level. The study protocol will typically require between 60 and 120 minutes. Throughout the study, a set of pre-defined stopping criteria will be monitored to ensure subject tolerance of the study procedures. These criteria are designed to be conservative safety measures and will result in study termination and provision of supportive care, as needed. Patient Safety Considerations: Extensive patient safety considerations minimizing the risks associated with implementation of this phase II design research protocol have been incorporated: 1. Many of the key eligibility (inclusions and exclusion) criteria reflect the deliberate selection of a premature infant population that is inherently less vulnerable and at lower risk of common morbidities of prematurity and less likely to suffer any adverse outcomes from implementation of the study procedures. a) I1. Corrected gestational age 27-35 weeks (GA): this selects a study population in which respiratory distress syndrome is common and CPAP is frequently used, while avoiding less mature infants with a CGA less than 27 weeks who are more prone to physiologic instability. We exclude this population in consideration of safety for this phase II study despite a high risk of CPAP failure and a potential for benefit from our long-term research goals of establishing methods to prevent CPAP failure. b) I2. Chronologic age of greater than 24 hours. This avoids study of infants during the first 24 hours of life when they may be more prone to physiologic instability. c) I3. On continuous CPAP support for greater than 24 hours. This prioritizes safety by restricting study to subjects demonstrating stability on CPAP therapy, in contrast to infants newly transitioned to CPAP without a period of demonstrated tolerance. d) I4. Supplemental oxygen requirement, with a fraction of inspired oxygen (FiO₂) 0.25 for at least 2 consecutive hours. This ensures that CPAP level changes are only performed in infants requiring supplemental oxygenation, suggesting V/Q mismatch and/or shunt from atelectasis. These subjects would plausibly benefit from carefully monitored changes in continuous distending airway pressure to counteract the pathophysiology resulting in the oxygen need. This criteria avoids CPAP

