
The following documents are currently attached to this item:

There are no documents attached for this item.

Deception

Does your project use deception?

No

International Research

Are you conducting research outside of the United States?

No

Analysis Plan

Results will be summarized using basic descriptive statistics. For Aim 1, a paired t-test for parametric results or a Wilcoxon signed-rank test for non-parametric results will be used to test our hypothesis that V/Q mismatch will improve at best CPAP level compared to baseline. For Aim 2, we will calculate the proportion of subjects in which best CPAP level is identified above the baseline pressure level to assess our hypothesis that this occurs in greater than 50% but less than 80% of subjects. Further, best CPAP for the cohort will be summarized as mean and standard deviation (if parametric) or median and interquartile range (if non-parametric). No formal statistical testing of significance will be performed for this second descriptive Aim. The change in V/Q over the two baseline periods, as well as the change in heart rate and blood pressure between baseline and best CPAP levels will be tested using the statistical approach as Aim 1. We predict the null hypothesis of no significant difference for these comparisons. Should a significant change in V/Q be identified between baseline periods, we will perform an additional analysis comparing the change in V/Q between baseline periods to the change in V/Q between baseline and best CPAP level to account for the independent impact of time on V/Q

mismatch. Confounding: key elements of our study design limit confounding for Aim 1, to measure the responsiveness of V/Q mismatch to a strategy of individualized CPAP level selection. The use of a pre-post within-patient analysis limits confounding from variation in between-patient characteristics. A remaining important source of confounding is the possibility that V/Q simply improves over time irrespective of CPAP pressure changes. We account for this by measuring V/Q on two separate occasions 30 minutes apart at baseline CPAP in the study protocol, facilitating an assessment of the stability of V/Q over time.

The following documents are currently attached to this item:

There are no documents attached for this item.

Data confidentiality

- Paper-based records will be kept in a secure location and only be accessible to personnel involved in the study.**

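### Aim 2 reads a 50–80% share of infants with best CPAP above baseline as support for individualised selection, but that share also depends on the clinician-set baseline and can mislead in either direction

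*Combined protocol and SAP*

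**What the plan says.** Under Objectives (Overall objectives), Aim 2 is to describe the distribution of best CPAP levels, in absolute terms and as steps from baseline. It is labelled exploratory and carries a numerical prediction: "we hypothesize that a best CPAP will be identified above the baseline in greater than 50% but less than 80% of subjects". The next sentence says what meeting it would mean: "Demonstrating that most but not all infants benefit from higher pressures will highlight the importance of individualized CPAP level selection in premature infants".

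The section on secondary outcomes states the underlying idea: "We hypothesize that best CPAP will vary between infants, resulting in a distribution of values".

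In the Analysis Plan, "we will calculate the proportion of subjects in which best CPAP level is identified above the baseline pressure level to assess our hypothesis". Best CPAP for the cohort is also to be summarised by mean and SD, or by median and interquartile range. No significance test is planned for this aim.

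On the reference level, the Procedures section says "V/Q will first be measured on two separate occasions 30 minutes apart at baseline CPAP, set by the clinical team", and the permitted step range is explained by "our institutional practice of typically setting a baseline CPAP level of 5 or 6" cm H₂O. The third inclusion criterion is wider: "On CPAP support between 4-8" cm H₂O. The documents do not give the expected split of baselines.

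**The concern.** The conclusion sought is about infants: that they differ in the pressure that suits them best. The statistic is about a difference between two things, the infant's best level and the level a clinician had already chosen. Variation in either one moves the share above baseline. A share between 50% and 80% can therefore arise because infants differ, because starting levels differ, or both, and the share alone cannot say which.

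At stake is the one sentence in the plan that turns a descriptive result into support for individualised CPAP. If it goes into the report as written, a cohort in which one fixed level suited everyone could be presented as evidence for individual titration, and a cohort with real differences could be presented as failing to show them.

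**Working it through.** **Inputs from the documents.** 20 evaluated infants (Accrual); window above 50% and below 80% (Objectives); baseline set clinically, typically 5 or 6, with 4–8 eligible (Procedures, Key inclusion criteria); steps from −2 to +3 within 3–8 cm H₂O; response threshold 5% (Procedures).

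**The plan's own figure.** The documents give no sample-size or power figure for Aim 2. The 20 infants come from Aim 1: d = 10/15 = 0.667, paired t-test, df = 19, two-sided 0.05. The noncentral t gives 80.7% power, so the stated 80% reproduces.

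**The window at n = 20.** 10/20 is exactly 50% and 16/20 is exactly 80%, so both are excluded. The window is 11 to 15 infants, and the chance of landing in it is P(11 ≤ X ≤ 15) for X binomial(20, p).

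**The true share.** With error-free readings, p = Σ P(baseline = b) × P(best = o), summed over all pairs with o > b. The baseline splits and best-level distributions below are assumptions. All best levels shown can be reached within the step limits.

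| Best levels | Baselines | Share above | P(11–15 of 20) |
|---|---|---|---|
| 6 in all infants (SD 0) | 65% at 5, 35% at 6 | 65% | 0.76 |
| 6 in all infants (SD 0) | all at 5 | 100% | 0 |
| 6, 7, 8 in equal thirds (SD 0.82) | all at 5 | 100% | 0 |
| 4, 5, 6 in equal thirds (SD 0.82) | all at 6 | 0% | 0 |
| 5, 6, 7 in equal thirds (SD 0.82) | all at 5 | 66.7% | 0.76 |
| uniform over 4–8 (SD 1.41) | all at 5 | 60% | 0.70 |
| uniform over 4–8 (SD 1.41) | all at 6 | 40% | 0.13 |

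Row 1 meets the window with no variation in best level. Rows 3 and 4 miss it despite real variation. Rows 6 and 7 have the same distribution of best levels, and only the starting level moves the share from inside the window to outside. Rows 2 and 5 are classified correctly.

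**Sensitivity to the baseline split.** With a common best level of 6, p is simply the share of infants starting at 5:

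| Share starting at 5 | 55% | 60% | 65% | 70% | 75% |
|---|---|---|---|---|---|
| P(11–15 of 20) | 0.57 | 0.70 | 0.76 | 0.72 | 0.57 |

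The probability is at least 0.50 for shares from about 53% to 77%.

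**Sensitivity to reading noise.** The stepwise procedure was simulated with an assumed 12% change in V/Q mismatch per cm H₂O and a noise SD of 10.6% per measurement. The SD of a difference is then 10.6 × √2 = 15.0%, equal to the value in the Aim 1 sample-size statement.

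- Row 1 falls to about 48% above baseline, P = 0.33.
- Row 3 falls to about 63% above baseline, P = 0.75.
- With no CPAP effect at all and baselines split evenly between 5 and 6, about 36% of infants are still classed as above baseline.

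At this noise level the contrast of 0.76 against 0 reverses. With 5% noise per measurement, rows 1 and 3 give 0.51 and 0.52. So noise changes the size and even the order of the probabilities.

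**Precision.** 13/20 (65%) has an exact 95% interval of 41% to 85%, wider than the window itself.

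**What a table by baseline would show.** In row 1 with 13 infants at 5 and 7 at 6, the shares above baseline are 13/13 (exact 95% CI from 0.025^(1/13) = 75% to 100%) and 0/7 (0% to 1 − 0.025^(1/7) = 41%), and every best level is 6. The table shows a single common level where the pooled 65% does not.

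**The case against.** The strongest reply is that Aim 2 is exploratory and untested, and that the verb used is only to highlight. No success claim, go/no-go decision or patient management hangs on the window. The plan also already promises best CPAP in absolute values and relative to baseline, with a measure of spread. In row 1 the absolute values would have SD 0, and in row 3 the steps would appear as +1, +2 and +3. An attentive reader of the results would see what the pooled share hides.

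Most of that stands. It limits the point to the inference tied to the window, since the data needed are already planned. It does not remove the point: the prediction is assessed by the share alone, neither of the other summaries enters that assessment, and no table of best level against baseline level is specified.

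A reader might infer something stronger: that the window is met whenever one level suits every infant and missed whenever best levels differ. The documents do not support that. Rows 2 and 5 are counter-examples, the baseline mix is not stated, and realistic noise can reverse the ordering. Nor does the case for individualised CPAP rest on this figure. It is argued in the Background, and the primary question is Aim 1.

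**Conclusion.** The point holds in a limited form. The share above baseline depends on the clinician-set baseline as well as on the infant's best level, so falling inside or outside 50–80% does not show whether best levels differ between infants. The share can meet the window with one common best level (probability 0.76 under an assumed 65/35 split and error-free readings) and miss it with truly different best levels (probability 0 for 6, 7 and 8 from a baseline of 5). These figures are illustrations: they rest on assumed baseline splits, assumed best-level distributions and no reading error. The dependence on baseline needs none of those particular values. Aim 1 is unaffected, and for an exploratory aim this is minor to moderate.

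**What to change.** In Objectives and the Analysis Plan:

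1. Keep the share of infants above baseline as description only, and stop drawing the importance of individualised selection from the 50–80% window.
2. Cross-tabulate absolute best CPAP by baseline CPAP, and report the share above baseline within each baseline level with exact 95% confidence intervals.
3. Base any statement about individualised selection on the spread of both absolute best levels and steps from baseline, read against the variability between the two baseline readings.

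No formal claim rule built on simulated models is needed; it would require dose-response inputs that the documents do not contain.

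The cost is a few sentences and one table. Baseline level, best level and both baseline readings are already collected, so no further infants or procedures are involved. The drawback is that, with 20 infants divided by baseline level, intervals will be wide and a statement in favour of individualised selection will be harder to support.

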Bronchopulmonary dysplasia (BPD) is a chronic lung disease resulting from premature birth that affects nearly 70% of infants born 28 weeks gestational age (GA) (1). BPD and its precursor, respiratory distress syndrome (RDS), are a leading cause of death in very premature infants (2). In turn, survivors require increased health expenditures and have adverse long-term respiratory and developmental outcomes in childhood (3-5). Despite the significant burden of BPD on pediatric health, very few preventive interventions exist (6). Of these, a strategy of minimizing mechanical ventilation (MV) with preferential initial nasal continuous positive airway pressure (CPAP) is the most novel (7-8). CPAP provides a continuous distending airway pressure, maintaining lung volumes and preventing atelectasis (a reduction in or collapse of the air sacs responsible for gas exchange) (9-10). This improves oxygenation by: a) reducing ventilation/perfusion (V/Q) mismatch (inefficient matching of lung areas receiving fresh air for gas exchange (ventilation) with lung areas receiving blood (perfusion) for gas exchange) and b) intrapulmonary shunt (blood passing from the right side of the heart through the lungs and to the body without any gas exchange). Sometimes, two levels of alternating pressure are applied in this way, with the higher and lower pressure levels alternating. This is called bi-level non-invasive support. When there is only one pressure level, this is the CPAP level. In bi-level support, the lower pressure level is considered the CPAP level. CPAP helps prevent BPD by providing these physiologic benefits while avoiding MV and subsequent ventilator induced lung injury (VILI), a key component in the pathogenesis of BPD. However, the benefit of preferential CPAP is modest. It is estimated that 1 death or case of BPD is averted per 25 treated infants (7-8). Consistent with this limited benefit, 46-83% of very premature infants at highest risk of BPD fail initial CPAP and nonetheless require MV (11-12). Oxygenation failure the result of excessive V/Q mismatch and shunt is the most frequent cause (12-14). An improved application of CPAP resulting in less oxygenation failure would further reduce death or BPD. A critical knowledge gap exists for a basic aspect of CPAP therapy: how much pressure should be used? There is a lack of evidence informing this question. Multi-center trials assessing CPAP versus MV have used pressures as disparate as 4-8 cm H₂O and have not specified how these were determined (11, 12, 15). While higher pressures applied to under-inflated lungs likely improve oxygenation, excessive pressure may result in over-distension, increasing the risk of harms such as air leak syndromes (12) or adverse cardiopulmonary interactions (16). We propose evaluating a novel physiologic approach for individualized CPAP level selection: identification of the lowest pressure level minimizing V/Q mismatch, a key contributor to poor oxygenation and CPAP failure. While traditional methods for measuring V/Q mismatch are invasive or technically burdensome (17-18), our research team has expertise in the use of a simple, non-invasive technique: a computerized oxygenation model enabling bedside quantification of V/Q mismatch (detailed within Methods) (19). In published research using this technique, our research team recently demonstrated a significant association between gestational age and the degree of V/Q mismatch, as well as high inter-rater reliability and validity with this approach for predicting BPD (20-21). Identification and application of an optimal pressure level by targeting a reduction in V/Q mismatch may improve oxygenation, decrease CPAP failure, avoid injurious MV and further reduce death or BPD (see Figure 1 in attached documentation). Table 1 summarizes existing prospective studies assessing the impact of CPAP level changes in premature

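### The readings that select best CPAP also form the primary outcome and non-responders score zero, so the test against zero does not have its stated 5% level

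*Combined protocol and SAP*

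**What the plan says.** - **Outcome** (Objectives, Primary outcome variable(s)): the improvement is "measured as the improvement in V/Q mismatch between the second baseline level and best identified CPAP level for each subject". For infants responding to neither +1 nor -1 cm H2O, "baseline CPAP will be defined as best, with zero assigned as the improvement in V/Q mismatch".
- **Selection rule** (Study Procedures, Procedures): "A positive response will be defined as an improvement in V/Q at the new pressure level of 5% relative to the preceding CPAP level". Secondary outcome variable(s) defines best CPAP through "an improvement greater than 5% in V/Q mismatch relative to the preceding CPAP level". The opening summary and Patient Safety Considerations instead express the response relative to baseline.
- **Downward branch** (Procedures): infants not responding at +1 "will return to baseline CPAP for 15 minutes and then be assessed at -1 cm" H2O. No V/Q reading is described at that return to baseline.
- **Test** (Analysis Plan): a paired t-test or, for non-parametric results, a Wilcoxon signed-rank test of best CPAP against baseline. No rule for choosing between them is given. Accrual states 20 evaluated infants, a 10% mean change, a 15% SD of the difference, 80% power and two-sided alpha 0.05.
- **Repeatability**: two baseline measurements 30 minutes apart serve to assess stability over time. Background reports "high inter-rater reliability and validity with this approach for predicting BPD", without a figure. Procedures averages up to four SpO2 values per pair, "acknowledging the inherent instability of pulse-oximeter values over time in premature infants".

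**The concern.** The level in the sample-size text is that of a paired difference that is free to take either sign. The outcome here is not such a difference. A chance-low reading at a new level, or a chance-high second baseline, makes an infant a responder and then counts as improvement. The opposite errors mostly lead to an assigned zero. If the -1 step is compared with the second baseline, every infant scores either zero or at least +5%, and no negative score can occur.

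Zero is a coherent value for a strategy that leaves an infant at baseline CPAP. The trouble lies in combining it with outcome readings that were themselves used for selection. At stake is what a significant primary result means in a phase II trial whose Design section says it is to determine whether there is a biologic effect.

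**Working it through.** **1. The plan's own figure.** Paired t-test, standardised effect 10/15, n = 20, df = 19, noncentrality (10/15)·√20 = 2.98. Power is 80.7% (78.5% at n = 19). The stated sample size reproduces, but for an unselected difference.

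**2. Inputs for the null check.** From the documents: n = 20; response at a 5% improvement; up-steps to +3 or a cap of 8 cm H2O; otherwise -1, then -2 with a floor of 3; outcome taken at the last responding level against the second baseline; zero for non-responders. Assumed: no CPAP or time effect; outcome as a percentage of the second baseline; baseline CPAP 5 cm H2O; independent normal reading error; -1 compared with the second baseline. The SD of the difference between two same-CPAP readings is also an assumption, shown as a range. One reading has SD = SD of difference/√2.

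**3. When the tests reject.** With only zeros and positive scores, the exact Wilcoxon test with zeros dropped gives p = 2·0.5^k for k responders: 0.063 at k = 5 and 0.031 at k = 6. It rejects when six or more of 20 respond. Noise alone makes 7.7% of infants respond at SD 3%, 25% at 5% and 45% at 10%. The binomial chance of six or more of 20 at those shares is about 0.3%, 38% and 94%, in line with the simulated rates below. For the t-test, four equal improvements among 20 already give p = 0.042.

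**4. Simulated null rejection, two-sided 0.05.**

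| SD of difference | Wilcoxon | t-test | Spurious mean (points) |
|---|---|---|---|
| 2% | 0% | 0% | 0.05 |
| 3% | 0.3% | 6% | 0.5 |
| 4% | 11% | 42% | 1.1 |
| 5% | 37% | 72% | 1.8 |
| 10% | 94-95% | 98% | 5.2 |

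The rate passes 5% at an SD of about 2.9% for the t-test and between 3.6% and 3.7% for Wilcoxon. A zero-heavy outcome would usually be judged non-normal, so Wilcoxon is the likely operative test. At SD 2% about 81% of null trials contain only zeros, and neither test can be computed.

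**5. Sensitivity (Wilcoxon / t-test).**
- Other comparators for -1: 0.3-0.5% / 3-4% at SD 3%, 37-44% / 55-62% at 5%, 80-87% / 83-89% at 10%. Up to 6.6% of infants then score negative.
- Noise shape at SD 5%: 25% / 57% with t-distributed error (5 df), 14% / 38% with infant-specific SDs.
- Zero-mean wander of the infant's own V/Q at SD 5%, making up 25-80% of the 30-minute difference variance: 53-68% / 81-87%.
- First or last responding level, preceding level or baseline as step comparator, and baselines of 4-7 cm H2O: 37-40% / 72-73% at SD 5%.

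**6. Does the plan already correct this?** The Analysis Plan tests the change between the two baselines and adds a further comparison only if that change is significant. Zero-mean error produces no mean change, so it would not normally trigger the extra analysis, yet it still feeds selection.

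**7. A contrast without selection.** The signed change from second baseline to +1 cm H2O, with negatives kept and no zeros assigned, rejects in 4.3-5.7% (t) and 3.8-5.8% (Wilcoxon) of null trials at SDs from 2% to 10%, with and without wander.

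**The case against.** The best reply is that the size rests on a figure the documents do not contain. Averaging SpO2 and fitting a curve through three pairs may make V/Q readings repeatable enough for the planned tests to be conservative. The remark on instability concerns pulse-oximeter values, and the averaging is the plan's response to it. At small noise the spurious mean is minor beside the hypothesised 10%. All of this stands. It does not restore the 0.05 level, which would be met only if repeatability happened to fall at the right value. Inter-rater reliability is not agreement between readings taken at different times.

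A reader might infer that the primary test is certainly inflated, or that any significant result would be spurious. The documents do not support that: below an SD of about 3% the tests are too strict, and nothing shows which side the trial is on. A reader might also infer that unfavourable error is always turned into zero. That is strict only if -1 is compared with the second baseline. Nor do the documents support replacing the primary inference with the +1 contrast, because the stated aim is individualised selection in either direction.

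**Conclusion.** The point holds and should be fixed in the analysis text. Selection and scoring share the same readings, non-responders score zero, and nothing in the plan corrects for it. Only the upward bias of the mean has a sure direction. The test level is not a property of the design: from well under 5% to above 90% over the assumed SD range of 2% to 10%. The rates assume no CPAP effect and independent normal error; heavier-tailed or infant-specific noise lowers them and within-infant wander raises them. Confidence is high for the direction of the bias in the mean and moderate for size.

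**What to change.** All of this uses readings the protocol already collects.

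1. Keep the best-CPAP improvement as the estimate for the strategy, but state that a significant test against zero is not by itself evidence of a CPAP effect.
2. Report the baseline-to-baseline SD with its interval. Judge the observed improvement against the noise-only improvement simulated from the plan's own step rule, carrying the uncertainty through. For example, an SD of 5% from 20 pairs has a 95% interval of 5·√(19/32.85) to 5·√(19/8.91), or 3.8% to 7.3%, and the benchmark is 1.8 points (1.0 to 3.4). State that wander makes the benchmark too low: at SD 5% it would be 2.7 points if half the variance were wander. This matters because "The study protocol will typically require between 60 and 120 minutes".
3. Add the signed percent change from second baseline to +1 cm H2O, in every infant assessed there, as a supportive analysis. Report how many infants were not assessed at +1 and why.
4. Reconcile the comparator wording across the opening summary, Secondary outcome variable(s), Procedures and Patient Safety Considerations, and state which reading the -1 step is compared with. The benchmark depends on it.

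**Cost.** Analysis wording and a short simulation, with no extra infants or readings. The claimed effect may shrink, and the noise SD rests on about 20 pairs. The +1 analysis answers a narrower question and misses infants who improve only at lower CPAP. With the planned SD of 15%, 20 infants give it 80% power for (2.093 + 0.861)·15/√20 = 9.9 points. If half the infants improve and half worsen by 10% at +1, its power is only 2-3%.
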